**NCT03851796**

**OCTOBER 13, 2025**

## STUDY PROTOCOL

We propose to conduct a 2x5 repeated-measures, randomized clinical trial to test study aims and hypotheses. We will randomly assign families to either: Parents as Coaches (PAC) or Parent Weight Loss (PWL). All adolescents will participate in the 4-month TEENS+ protocol. The proposed intervention is modeled after our pilot and designed to test its efficacy in a fully powered trial over 1-year follow-up. Assessments will be conducted at 0, 2, 4, 8 and 12 months (m). The primary dependent variable of interest is  $\Delta$ BMI at 12m ( $\Delta$ BMI4-12m), representing adolescent weight loss maintenance. Eight waves of adolescent/parent dyads will be stratified by sex and race and randomized to TEENS+PAC or TEENS+PWL. We will recruit 210 families (105 randomly assigned to each condition) using established strategies, and employ a block randomization scheme, stratified for adolescent sex and race, to ensure equal group allocation on these variables. Participants who consent/assent, meet eligibility criteria and complete baseline assessments will be eligible for randomization and assigned to either TEENS+PAC or TEENS+PWL. To reduce contamination, adolescents will be in groups according to their parents' assignment. Participants will be informed of their intervention assignment at the first group meeting.

**TEENS+ Adolescent Intervention.** TEENS+ was informed by the integration of theory and previous research. After baseline, families will be randomized to TEENS+PAC or TEENS+PWL. All adolescents participate in TEENS+. Adolescent groups are single-sex, to facilitate interaction at this critical developmental stage, led by 2 trained, supervised lifestyle coaches (psychology doctoral trainee paired with a registered dietitian), *masked to study hypotheses*. Over 16 weeks, adolescents meet weekly for 1-hour groups. Content in TEENS+PAC and TEENS+PWL is identical; however, in PAC, adolescents alternate weekly between concurrent, separate group visits and conjoint (parent and child) group nutrition education visits. In PWL, all core adolescent groups occur separately from their parents. TEENS+ considers the adolescent developmental tasks of individuation and autonomy development, and includes strategies to navigate peer influences, while also eliciting adolescent-driven reasons for change. TEENS+ recognizes that responsibility for eating choices shifts from parents to adolescents, yet acknowledges that parent influence remains strong (e.g., ~50% of adolescents eat  $\geq$ 5 meals/week with their family). As such, autonomy is emphasized, and adolescents are also encouraged to consider what they need from significant others (including parents) for successful goal attainment (e.g., asking parents to keep certain foods in/out of the home; transportation to the YMCA).

Manualized sessions follow a behavior therapy approach, including guided goal-setting, self-monitoring, identifying barriers and solutions, contingency management, stimulus control, dealing with setbacks, maintenance and relapse prevention. Weight is assessed weekly by the coaches, with MI-consistent, autonomy-supportive feedback provided. Weekly food and physical activity (PA) logs are maintained and reviewed by coaches, with personalized, written feedback provided. A point system (1 raffle ticket/point) is implemented to reinforce attendance and log completion, consistent with behavior theory. Raffles are drawn on a variable reinforcement schedule. Group incentives (e.g., water bottles) are provided monthly. In these ways, TEENS+ facilitates group cohesion and reinforces adherence and attendance, increasing engagement. Families also attend a cooking class and receive YMCA memberships. In the maintenance phase (4-12m), monthly, arm-specific newsletters are mailed to participants to reinforce content and maintain engagement with the trial.

Adolescents have 4 motivational interviewing (MI)-based, 30-min individual visits. In month 1, adolescents meet with their behavior coach for a values exploration exercise to explore the consistency of TEENS+ with adolescents' goals and values, to increase internal motivation for change and treatment engagement. In months 2 and 3, adolescents meet with their dietitian for personalized nutrition education. The final behavior visit (month 4) includes development of a personalized relapse prevention and maintenance plan, linking weight loss maintenance to adolescents' goals and values. These visits also serve to monitor emergence of psychopathology.

MI is integrated into both group and individual sessions, based on findings from *MI Values*, in which 2 MI sessions enhanced TEENS treatment engagement, retention, and diet, compared with a control group. [name] will use methods previously described to train coaches and maintain fidelity to MI. Specific MI strategies include: normalize ambivalence, highlight autonomy, elicit adolescents' personal reasons for change (and normalize that these might differ from those of their parents and other participants), and relate weight loss to participant-stated values and goals. Coaches empathize with difficulties involved in making behavior changes, while building adolescent self-efficacy. Last, information is presented collaboratively, to avoid the "expert role," reduce discord and enhance engagement.

The TEENS+ dietary intervention was designed to result in a caloric deficit via adding low calorie, nutrient-dense foods ("Go Foods") while remaining within a prescribed calorie limit. Within the context of the Traffic Light Diet with a calorie goal, Epstein et al. found that targeting an *increase in healthy foods* vs. a *reduction in unhealthy foods* was associated with greater BMI reduction (among younger, primarily white children). Importantly, interventions targeting an increase in fruits and vegetables in the absence of a calorie goal *did not* result in a reduction of fat and sugar. Consequently, individual calorie (1200-1400 for girls and 1500-1800 for boys) and Go Food goals are provided and adjusted as needed throughout treatment. Calorie goals were determined based on our pilot baseline data, which suggested that these prescriptions will result in  $\geq 500$  kcal/day deficit, to result in a 1-2lb/week weight loss. Go Food goals are individualized based on baseline food records, and increased as previous goals are met. Standardized lessons provide education about energy balance, calories, macronutrients, and high-risk eating behaviors associated with obesity, coupled with evidence-based behavioral strategies to help adolescents implement changes. In these ways, participants add healthy foods (and must reduce unhealthy foods to remain within calorie goals) while losing weight.

The TEENS+ PA intervention includes identifying strategies to achieve  $\geq 1$  hr/day of moderate PA (tracked in logs); PA can occur at the HLC, YMCA, or other location, with a focus on free/low-cost, realistic strategies to promote sustainable PA. Adolescents are required to exercise  $\geq 1$  x/week at the HLC gym (30min of resistance training; 30min of cardiorespiratory exercise). During HLC exercise sessions, participants wear heart rate monitors (E600 Polar Electro, Inc.) and are encouraged to maintain a heart rate  $> 150$  beats/min during the aerobic portion. TEENS+ includes setting goals and learning strategies to achieve  $\geq 1$  hour/day of moderate PA. Adolescents are provided a progression that gradually increases the frequency and duration of PA, with a prescribed weekly duration of vigorous PA. We successfully implemented this protocol in the TEENS+ pilot.

**Parent Interventions.** Parents will participate in their assigned, *distinct* intervention (PAC/PWL), matched on contact, led by trained, supervised lifestyle coaches (psychology doctoral trainee and registered dietitian), with different leaders from the adolescent treatments to minimize potential contamination.

**a. Parents as Coaches (PAC):** PAC focuses on parent skills training to support their adolescents' weight management. It includes combined nutrition education sessions with adolescents as well as independent parent skills training group sessions, delivered while adolescents are in their own BWL groups. In these ways, PAC capitalizes on adolescent autonomy and independence, while acknowledging the need for parent support and involvement. Parents are taught authoritative parenting (providing structure with warmth), and how to apply this to weight management (e.g., setting limits around food kept in the house). PAC teaches positive reinforcement principles to promote behavior change, the importance of role modeling, and communication about eating and weight. Throughout, developmentally appropriate strategies to promote adolescent behavior change are emphasized. For example, most adolescents need some assistance (at least initially) to self-monitor caloric intake accurately. Parents are taught to collaborate with their adolescent to determine optimal strategies for assisting with this task (highlighting its consistency with adolescents' goals). This approach reduces adolescent resistance and increases autonomy, while also enhancing skill development. As skills are demonstrated, parents provide positive reinforcement, and re-negotiate the level of assistance needed. In PAC, parents' own weight management is not specifically addressed and parent weight is not monitored. However, PAC emphasizes parents' roles as important models of health behaviors, the value of healthy eating and exercise for the entire family (regardless of weight), and the importance of setting up the home environment to facilitate their adolescents' successful goal attainment. PAC also emphasizes the critical need for all caregivers to use consistent feeding strategies and teaches parents how to be assertive in communicating these concerns. PAC teaches parents to be agents of change for the family and to promote consistent feeding and eating behaviors for all family members, including siblings and other caregivers.

Parents set specific goals each week, related to achieving PAC treatment targets, which focus efforts on areas within their control to impact adolescent behavior. Specifically, parents maintain a daily log to self-monitor: the number of meals planned and prepared at home for their adolescent; whether they reviewed their adolescents' logs; responsibility for adolescent logging (parent/child/combined); and provision of Go Food and PA opportunities for their adolescent. Progress on goals is reviewed weekly, facilitating group brainstorming of strategies to overcome barriers and positively reinforce successes. Behavior coaches also deliver personalized coaching in brief individual check-ins before group, and examine the relation between parental behaviors and their adolescents' behaviors and weight change, guiding adjustments as needed to assist in goal attainment. Parent coaches also observe TEENS+ sessions, to facilitate integration of content between the adolescent and parent treatments. In these ways, coaches guide parents to focus on empirically-supported strategies within their control to foster healthy behavior changes in adolescents.

**b. Parent Weight Loss (PWL):** In PWL (developed based on [name] NIH trials), parents participate in a 16-week adult BWL program, concurrent, yet independent from their adolescents. Monthly activities

(common across both arms) foster shared engagement in BWL strategies between parents and adolescents (i.e., cooking class, YMCA orientation, recipe makeover, and final celebration). Consistent with adult BWL, the goal is to produce parent weight losses of 5-7% during the 4m program. Participants receive daily calorie and fat gram goals based on initial weight, designed to yield 1-2lb/wk weight loss, with education about energy balance, diet quality, and calories in macronutrients provided. They are instructed to self-monitor weight, dietary intake and PA within the context of a self-regulation framework that teaches them to use this information to evaluate their behavior and make adjustments as needed to assist in goal attainment. Parents are trained in core evidence-based behavioral strategies (e.g., goal-setting, problem solving, stimulus control) to help them meet their own diet and PA goals. The adapted BWL program also includes specific content focused on navigating financial, environmental, social and emotional barriers to weight management, and implementation planning is conducted weekly in group to develop personalized plans for goal attainment. Further, MI is integrated into PWL, consistent with [name] previous weight loss trials. Weight is measured weekly in a brief individual check-in prior to group, and feedback is provided in an MI-consistent manner. Parents also receive weekly personalized feedback from their coaches on their food diaries.

Participants are encouraged to consume a heart healthy diet (low in saturated/trans-fats and rich in fruits/vegetables/whole grains). Nutrition education in PWL is consistent with that taught to adolescents with key distinctions: 1) more emphasis on reducing saturated fat as a strategy to meet calorie goals; 2) more focus on energy density; and 3) parents do not receive Go Food goals. However, to maximize use of shared strategies, PWL emphasizes consuming Go Foods within the context of diet quality and energy density, to assist in increasing satiety and adherence to calorie goals. Participants are instructed to gradually increase PA until achieving  $\geq 250$  min/wk of moderate intensity PA. The importance of both structured PA and lifestyle activity is stressed. Typical barriers to PA are discussed, and suggestions for exercise that incorporate activities of daily living are presented. Note that PWL does not focus on how to support adolescents' weight loss directly (although emphasizes that concurrent engagement in these behaviors should be helpful for their adolescent).

### **Assessments.**

Assessments of anthropometrics, dietary intake, PA, parenting and home environment variables will be completed by trained, masked assessors at 0, 2, 4, 8, and 12m, with the primary endpoint at 12m follow-up. Measures for parents and adolescents include the following: anthropometrics (after a 12 hour fast), dietary intake, physical activity, parenting style, eating disorders and depression, parent/child conflict, weight control strategies (physical activity, dietary behaviors, and self-monitoring), Parents will also complete measures assessing demographics, child feeding behaviors, the home food and home exercise environments, self-efficacy to support their child's healthy weight management, and readiness to change. Adolescents will also complete measures assessing perceived autonomy support from their parents, family social support for eating and exercise, and perceptions of parent's dieting behaviors. Parents and adolescents will complete exit surveys at the end of treatment (4 month). Attendance and adherence to program components will be monitored, and interventionists will maintain fidelity checklists after each session. Formal fidelity monitoring will also be conducted.

## Statistical Analysis Plan

**Analyses** will be conducted with SAS v9.4 and Mplus. Descriptive statistics will be generated for outcome variables and potential covariates according to PAC/PWL. Non-normally distributed variables will be transformed and between-group baseline differences for outcomes and covariates will be assessed. All study hypotheses will be tested using Intent-To-Treat (ITT) methods, with multiple imputation incorporating auxiliary variables used to handle missing data, and all primary analyses will be performed using imputed data sets. We will also conduct additional, less conservative complete-case analyses and we will compare these results to the ITT analyses.

For **Aim 1**, the primary outcome is between-group (PAC vs. PWL) differences in adolescent  $\Delta\text{BMI}_{4-12m}$ . Both within- and between-group effects of treatment on  $\Delta\text{BMI}_{4-12m}$  will be compared via linear mixed model analyses. This model will also be used for **Secondary Aim** analyses, to examine within- and between-group changes in adolescent energy intake (kcal/d); energy expenditure (kcal/d); and PA (min/wk) from 4-12m. For **Aim 2**, both within- and between-group effects of treatment on parental variables, home food and exercise environment, and adolescent perceived autonomy support from 0-4m will be compared via linear mixed model analyses. Multivariate linear regressions will examine the impact of 0-4m changes in these variables on adolescent weight loss maintenance ( $\Delta\text{BMI}_{4-12m}$ ). We will then evaluate whether the treatment effects for weight loss maintenance are mediated by *authoritative parenting* using Structural Equation Modeling (SEM). Model fit will be compared using chi-square analyses. To evaluate whether BE/LOC moderates the effects of treatment on authoritative parenting and/or authoritative parenting on weight loss maintenance, we will apply a moderated mediation model by adapting the SEM model above using a multiplicative regression approach. In the **Exploratory Aim**, we will evaluate the effect of concordance of parent and adolescent variables on adolescent weight loss maintenance using linear mixed models. Concordance will be defined by the possible response pairs or using difference scores for categorical and continuous variables, respectively.

**Power analyses** were conducted using SD and effect sizes from the pilot for between-group (PAC/PWL)  $\Delta\text{BMI}_{7m}$ , projected to 12m (the primary endpoint of this trial;  $\Delta\text{BMI}_{4-12m}$ ). We assumed a constant rate of weight change and increased SD. A proposed sample size of 210 (105 dyads per arm) will have >80% power (2-sided, alpha=.05) to detect significant *between-group* differences in adolescent  $\Delta\text{BMI}_{4-12m}$ , with SD≤2.9, which corresponds to a small to moderate effect size (Cohen's  $d=.39$ ). The 12m projections, with SD≤1.7, and N=210 provide 80% power to test BE/LOC as a moderator. This sample size also provides 80% power to evaluate authoritative parenting as a mediator in a partially mediated model. We used effect sizes to power this trial given lack of agreed-upon clinically significant thresholds for adolescent BMI change.

Protocol Changes		
DATE	CHANGE	REASON
June 2018	Modified adolescent baseline calorie goal ranges. Throughout the intervention, baseline female calorie range goals ranged from 1200-1400 to 1700-1900. Baseline male calorie range goals ranged from 1400-1600 to 2400-2600.	Enhanced specificity based on starting height and sex.
March 2020	
 
1. Intervention sessions transitioned from in-person to virtual (Zoom) due to COVID-19.
 
2. Exercise program transitioned from in-person to pre-recorded exercise workout videos provided on a private YouTube channel for participants accessible from study website. Heart rate monitors were no longer worn.
 
3. Transitioned to remote assessments due to restrictions. Calibrated scales and stadiometers were left on participants' porches with video instructions on obtaining height and weight measurements. Recalls were conducted over Zoom.
 
4. Cooking classes transitioned to virtual. Participants were provided a gift card and ingredient list to purchase supplies needed prior to classes led by chefs.
 
	COVID-19 restrictions and mandates
August 2020	Resumed in-person assessments but continued to offer remote assessments. Remote assessments transitioned to being conducted by assessor in the participant home (or designated location) as an option to accommodate families' comfort level.	Virginia now in Phase 3 of re-opening. In-person interactions permitted with proper protections in place.
September 2020	Exercise program transitioned to live group workouts via Zoom. Group exercise sessions occurred on respective group nights (Mon-Thurs) and on Saturday mornings which were treatment arm specific. Pre-recorded exercise videos still available on private YouTube channel accessible from study website.	To increase participant engagement and attempt to mimic in-person style workout approach.
February 2021	Virtual group exercise sessions transitioned to being offered two nights per week-- one night for each treatment group. Four virtual one-on-one personal training sessions were offered to each participant to use throughout the 16-week intervention. Pre-recorded exercise videos still available on private YouTube channel accessible from study website.	Group exercise engagement and attendance was low. One-on-ones were added increase interest and engagement.
October 2023	
 
1. Exercise program included the option of in-person personal training sessions (4) in addition to the previously offered Zoom sessions (4 sessions max in either format). Group exercise session format remained the same. Cooking class was offered in-person and virtually.
 
	Participants eager for in-person interactions. COVID-19 concerns no longer as relevant.

Assessment Measure Changes		
DATE	CHANGE	REASON
January 2020	
 
1. Changed Food Security (FS) questionnaire from the 6-item version to the 18-item version.
 
2. Added the Perceived Stress Scale (PSS) questionnaires to both parent and adolescent assessments.
 
	
 
1. Full measure provides a more comprehensive level of food security.
 
2. Stress was an important variable to examine given its relation to obesity and within the current context of the COVID-19 pandemic
 

July 2020	
 
1. Adolescent questionnaires were modified to ask about the participating parent, only, in the following questionnaires at assessments:           
 
a. Family Experiences Related to Food (FERFQ)
 
b. Perceived Parental Autonomy Support Scale (P-PASS)
 
 
 
2. The Conflict Behavior Questionnaire (CBQ) questionnaire was removed from both parent and adolescent assessments.
 
3. The FERFQ was modified to only include questions regarding modeling of dieting behaviors
 
	Reduce participant burden considering additional demands on families' lives in the context of the COVID-19 pandemic; removed variables not directly associated with study aims.
January 2021	
 
1. Removed Parent Readiness to Change (PRC) questionnaire from parent assessments.
 
2. Removed Parent Efficacy for Child Healthy Weight Behavior (PECHWB) questionnaire from parent assessments.
 
	Reduce participant burden and measures not required for testing conceptual model.
January 2021	The Conflict Behavior Questionnaire (CBQ) questionnaire was added back for both parent and adolescent assessments. Adolescents were only asked about the participating parent.	Perceptions of parent/adolescent conflict was an important variable to continue to examine.
June 2022	Added the Standardized Screening Tool for Health questionnaire at all assessment time points	Expanded assessment as part of ancillary project and given greater burden of social determinants of health in context of pandemic.

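### The mediation model names authoritative parenting as its only mediator; parent weight change, PWL's measured target, should be a parallel mediator in a second prespecified model

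*Combined protocol and SAP*

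**What the plan says.** The Statistical Analysis Plan (Aim 2) states "We will then evaluate whether the treatment effects for weight loss maintenance are mediated by" authoritative parenting, using SEM. The BE/LOC moderated mediation is adapted from the same model. The power paragraph adds: "This sample size also provides 80% power to evaluate authoritative parenting as a mediator in a partially mediated model". A partially mediated model keeps a direct path from treatment to outcome. The plan states no second mediator, no adjustment for mediator-outcome confounders and no sensitivity analysis for the SEM.

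The Parent Interventions section gives the arms different parent targets:

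- **PAC:** "Parents are taught authoritative parenting (providing structure with warmth"). Parents' "own weight management is not specifically addressed and parent weight is not monitored" in this arm.
- **PWL:** "the goal is to produce parent weight losses of 5-7% during the 4m program". The section also says: "Note that PWL does not focus on how to support adolescents' weight loss directly". It then qualifies this with the message that PWL gives to parents: "although emphasizes that concurrent engagement in these behaviors should be helpful for their adolescent".

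The Assessments section schedules visits at 0, 2, 4, 8 and 12 months and says: "Measures for parents and adolescents include the following: anthropometrics (after a 12 hour fast"). Parent weight change from 0 to 4 months is therefore available in both arms.

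Before the SEM, Aim 2 compares the arms on a group called parental variables, the home environment and perceived autonomy support, and regresses adolescent BMI change on their 0-4 month changes. The term parental variables is not defined, so the reader cannot tell whether parent weight is among them.

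**The concern.** Randomizing families makes the arm-to-parenting path a fair comparison. It does nothing for the parenting-to-BMI path, because parents are not randomized to how much their parenting changes. Any other parent change that moves with parenting within an arm, and also affects the adolescent, is partly credited to parenting or partly cancels it. Parent weight change is the obvious candidate: one arm is built to produce it, PWL parents are told that their own engagement should help the adolescent, and it is measured on the mediator's 0-4 month window.

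The trial's statement about mechanism is at stake, together with the moderated mediation built on it. A parenting effect could be declared when there is none, or missed when there is one. Separately, whatever PWL does at arm level goes into the direct path, and the planned model leaves it there unexplained.

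**Working it through.** **Stated power.** With 105 per arm, d = 0.39 and two-sided alpha 0.05, power for the primary comparison is 80.7% (normal approximation) or 80.3% (noncentral t). The stated figure of more than 80% reproduces. The 80% mediation power cannot be reproduced because no path values are given. Assumed arm-to-parenting and parenting-to-BMI paths of 0.39 and 0.39 SD give 80%; 0.4 and 0.2 give 67%.

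**Inputs.** From the documents: 210 dyads, 105 per arm, alpha 0.05, a direct path in the model. Assumed, because the documents are silent: an arm effect on parenting of 0.5 SD, an effect *b* of parent weight loss on adolescent BMI change of 0.2 or 0.3 SD per SD, a within-arm correlation *r* between the two parent changes, residual SD 1, no dropout. Mediation is declared when arm-to-parenting and parenting-to-BMI (given arm) are both significant.

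**Bias.** With both parent changes in within-arm SD units, and arm in the model, the bias in the parenting-to-BMI path is *b* × *r*. It is zero when *r* = 0.

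**False mediation at r = 0.3, true parenting effect zero.**

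- Arm-to-parenting: SE = √(2/105) = 0.138; z = 0.5/0.138 = 3.62; power 0.952.
- *b* = 0.3: bias 0.3 × 0.3 = 0.09; SE = √(1 + 0.09 × 0.91)/√207 = 0.0723; z = 1.245; rejection probability 0.238; joint 0.238 × 0.952 = 0.226.
- *b* = 0.2: bias 0.06; SE = 0.0708; z = 0.848; rejection probability 0.136; joint 0.129.

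Simulation (4000 trials per setting) gave 22.6% and 12.7%; a further run gave 12-22%. Simulated rates across correlations:

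| r | Parenting alone | Parent weight added |
|---|---|---|
| 0 | about 5% | about 5% |
| 0.1 | about 6% | 4-6% |
| 0.2 | 9-12% | about 5% |
| 0.3 | 13-23% | about 5% |
| 0.5 | 29-52% | about 5% |

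**Masking.** Take a true parenting effect of 0.25 SD per SD in the favourable direction, *b* = 0.3 and *r* = -0.3. The net path is 0.25 - 0.09 = 0.16; z = 0.16/0.0723 = 2.21; joint power is about 57%. With parent weight in the model, SE = 1/√(206 × 0.91) = 0.0730; z = 3.42; joint power is about 88%. Simulation gave 57% against 88%; a further run gave 56% against 86%.

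**Does it depend on PWL being active?** At *r* = 0.3 and *b* = 0.3, the simulated false-mediation rate was 22.5% with no arm effect on parent weight, 22.0% with a 0.8 SD shift one way and 22.5% with 0.8 SD the other way. It does not.

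**Limit of the remedy.** Suppose shared parent engagement is the source of *r* = 0.3 and also acts directly on adolescent BMI by 0.2-0.3 SD, with *b* = 0.2. The two-mediator model then still declares false mediation in about 20-37% of trials, against 61-81% with parenting alone.

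**Cost in power.** With a true parenting effect of 0.25, no parent-weight effect and *r* = 0.3, joint power falls from about 90% (z = 0.25 × √207 = 3.60) to about 88% (z = 3.42), or 2 points.

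**The case against.** Testing one hypothesised mediator is legitimate, and this is a secondary, mechanistic analysis. Three stronger readings are tempting, and the documents do not support them.

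- *The parenting path absorbs PWL's effect because PWL is an active arm.* The model is partially mediated, so PWL's arm-level effect goes to the direct path. The false-mediation rate is the same with or without an arm effect on parent weight. What remains is mediator-outcome confounding, which would arise with an inert comparator too.
- *The trial cannot explain why the arms differ, and a null result would hide two offsetting mechanisms.* Direct and indirect effects are estimated separately, so opposite signs would show, though the direct part would have no label. The other Aim 2 regressions and the concordance analyses also bear on mechanism, although they estimate no indirect effects.
- *PWL is stated to work through parent weight.* The protocol gives parent weight loss as PWL's target and tells parents that shared behaviours should help. The route from parent weight to adolescent BMI is an inference. PAC also promotes parental role modelling and healthy eating for the whole family, so opposite directions in the two arms are not established.

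Two further objections stand. No passage supports a particular within-arm correlation, in size or sign. And adding parent weight is not a complete cure: shared engagement can still bias the parenting path, and if parenting itself changes parent weight, a parallel model moves that part of parenting's effect to the weight path. Both points shape the fix. They do not remove the reason for it.

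**Conclusion.** The concern holds in conditional form. The SEM names one mediator, although the other arm's target is measured over the same window. The parenting path is biased if the two parent changes are correlated within arm and parent weight affects adolescent BMI; without that correlation there is no bias from this source. Under the assumed values, false parenting mediation is about 12-22% at *r* = 0.3, against about 5% with parent weight modelled. At *r* = -0.3, power for a real effect is about 56-57% against 86-88%. Every correlation and path value is an assumption. The between-arm comparison of adolescent BMI change is unaffected. This is an inexpensive improvement to Aim 2, not a flaw in the trial's main result.

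**What to change.** In the Statistical Analysis Plan, Aim 2:

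1. Keep the single-mediator SEM for authoritative parenting as the hypothesised model.
2. Add a second, prespecified SEM with the parent's 0-4 month change in BMI (or percent weight) as a parallel mediator, residuals allowed to correlate.
3. Report both indirect effects, and the parenting-to-BMI path with and without parent weight.
4. Add a sensitivity analysis for remaining mediator-outcome confounding.
5. Define parental variables and list the SEM covariates.

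The second model needs one more variable in Mplus and no new data. It costs about 2 points of power for the parenting path at *r* = 0.3. If parenting changes parent weight, the parallel model reassigns that part of the effect, which is why both models should be reported side by side.
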